14.2 Analyses of Efficacy

Table 14.2.1.1
Summary of Best Overall Response, Objective Response Rate, and Clinical Benefit Rate - Dose Escalation
Efficacy Evaluatable Analysis Set

	WTX-330 0.016 mg/kg (N=x)	WTX-330 0.032 mg/kg (N=x)	WTX-330 0.056 mg/kg (N=x)	WTX-330 0.084 mg/kg (N=x)	WTX-330 0.126 mg/kg (N=x)	WTX-330 0.190 mg/kg (N=x)	WTX-330 0.290 mg/kg (N=x)	WTX-330 0.XXX mg/kg (N=x)	Total (N=xX)
RECIST 1.1									
BOR, n(%)									
Complete Response (CR)	X (XX.X)	XX (XX.X)							
Partial Response (PR)	X (XX.X)	XX (XX.X)							
Stable Disease (SD)	X (XX.X)	XX (XX.X)							
Progressive Disease (PD)	X (XX.X)	XX (XX.X)							
Not Evaluable	X (XX.X)	XX (XX.X)							
ORR n(%)	X (XX.X)	XX (XX.X)							
95% exact CI, %	XX.X,XX.X	XX.X,XX.X							
CBR at 3 month, n(%)	X (XX.X)	XX (XX.X)							
95% exact CI, %	XX.X,XX.X	XX.X,XX.X							
CBR at 6 month, n(%)	X (XX.X)	XX (XX.X)							
95% exact CI, %	XX.X,XX.X	XX.X,XX.X							
CBR at 9 month, n(%)	X (XX.X)	XX (XX.X)							
95% exact CI, %	XX.X,XX.X	XX.X,XX.X							
iRECIST									
iBOR, n(%)									
iCR	X (XX.X)	XX (XX.X)							
iPR	X (XX.X)	XX (XX.X)							
iSD	X (XX.X)	XX (XX.X)							
iUPD	X (XX.X)	XX (XX.X)							
iCPD	X (XX.X)	XX (XX.X)							
Not Evaluable	X (XX.X)	XX (XX.X)							
iORR, n(%)	X (XX.X)	XX (XX.X)							
95% CI, %	XX.X,XX.X	XX.X,XX.X							
iCBR at 3 month, n(%)	X (XX.X)	XX (XX.X)							
95% CI, %	XX.X,XX.X	XX.X,XX.X							
iCBR at 6 month, n(%)	X (XX.X)	XX (XX.X)							
95% exact CI, %	XX.X,XX.X	XX.X,XX.X							
iCBR at 9 month, n(%)	X (XX.X)	XX (XX.X)							
95% exact CI, %	XX.X,XX.X	XX.X,XX.X							

Note: Best overall response (BOR) of CR and PR per RECIST 1.1 needs to be confirmed in a subsequent assessment (≥ 4 weeks). Immune Best overall response (iBOR) per iRECIST 1.1 is the best response among all visits according to the following sequence: Immune Complete Response (iCR), Immune Partial Response (iPR), Immune Stable Disease (iSD), Immune Confirmed Progressive Disease (iCPD), Immune Unconfirmed Progressive Disease (iUPD), Not Evaluable.

Protocol: WTX-330x2101

Date: 26Feb2025

Note: Overall response rate (ORR or iORR) is defined as the proportion of patients achieving CR and/or PR in RECIST 1.1 or iCR and/or iPR in iRECIST.

Note: Clinical Benefit Rate (CBR or iCBR) is defined as the proportion of subjects achieving clinical benefit, which is defined as the time from the date of last CR/PR/SD per RECIST or iCR/iPR/iSD per iRECIST to the date of first dose is at least 3, 6, or 9 months.

Table 14.2.1.2.1
Summary of Best Overall Response, Objective Response Rate, and Clinical Benefit Rate - Dose Expansion
Efficacy Evaluatable Analysis Set

	Arm A (N=XX)	Arm B [1] (N=XX)	Total (N=XX)
RECIST 1.1			
BOR, n(%)			
Complete Response (CR)	X (XX.X)	X (XX.X)	XX (XX.X)
Partial Response (PR)	X (XX.X)	X (XX.X)	XX (XX.X)
Stable Disease (SD)	X (XX.X)	X (XX.X)	XX (XX.X)
Progressive Disease (PD)	X (XX.X)	X (XX.X)	XX (XX.X)
Not Evaluable	X (XX.X)	X (XX.X)	XX (XX.X)
ORR n(%)			
95% exact CI, %	XX.X, XX.X	XX.X, XX.X	XX.X, XX.X
CBR at 3 month, n(%)	X (XX.X)	X (XX.X)	XX (XX.X)
95% exact CI, %	XX.X, XX.X	XX.X, XX.X	XX.X, XX.X
CBR at 6 month, n(%)	X (XX.X)	X (XX.X)	XX (XX.X)
95% exact CI, %	XX.X, XX.X	XX.X, XX.X	XX.X, XX.X
CBR at 9 month, n(%)	X (XX.X)	X (XX.X)	XX (XX.X)
95% exact CI, %	XX.X, XX.X	XX.X, XX.X	XX.X, XX.X
iRECIST			
iBOR, n(%)			
iCR	X (XX.X)	X (XX.X)	XX (XX.X)
iPR	X (XX.X)	X (XX.X)	XX (XX.X)
iSD	X (XX.X)	X (XX.X)	XX (XX.X)
iUPD	X (XX.X)	X (XX.X)	XX (XX.X)
iCPD	X (XX.X)	X (XX.X)	XX (XX.X)
Not Evaluable	X (XX.X)	X (XX.X)	XX (XX.X)
iORR, n(%)			
95% CI, %	XX.X, XX.X	XX.X, XX.X	XX.X, XX.X
iCBR at 3 month, n(%)	X (XX.X)	X (XX.X)	XX (XX.X)
95% CI, %	XX.X, XX.X	XX.X, XX.X	XX.X, XX.X
iCBR at 6 month, n(%)	X (XX.X)	X (XX.X)	XX (XX.X)
95% exact CI, %	XX.X, XX.X	XX.X, XX.X	XX.X, XX.X
iCBR at 9 month, n(%)	X (XX.X)	X (XX.X)	XX (XX.X)
95% exact CI, %	XX.X, XX.X	XX.X, XX.X	XX.X, XX.X

Note: Arm A = Patients with indications for which a CPI is indicated/approved; Arm B = Patients with tumor types for which CPI therapy is not indicated/approved.

Note: Best overall response (BOR) of CR and PR per RECIST 1.1 needs to be confirmed in a subsequent assessment (≥ 4 weeks). Immune Best overall response (iBOR) per iRECIST 1.1 is the best response among all visits according to the following sequence: Immune

Protocol: WTX-330x2101

Date: 26Feb2025

Complete Response (iCR), Immune Partial Response (iPR), Immune Stable Disease (iSD), Immune Confirmed Progressive Disease (iCPD), Immune Unconfirmed Progressive Disease (iUPD), Not Evaluable.

Note: Overall response rate (ORR or iORR) is defined as the proportion of patients achieving CR and/or PR in RECIST 1.1 or iCR and/or iPR in iRECIST.

Note: Clinical Benefit Rate (CBR or iCBR) is defined as the proportion of subjects achieving clinical benefit, which is defined as the time from the date of last CR/PR/SD per RECIST or iCR/iPR/iSD per iRECIST to the date of first dose is at least 3, 6, or 9 months.

[1] Include solid tumor only.

Table 14.2.1.2.2
Summary of Best Overall Response, Objective Response Rate, and Clinical Benefit Rate
- Dose Expansion by Type of Disease (Solid Tumor)
Efficacy Evaluable Analysis Set

	Arm A				Arm B	
	RCC (N=x)	NSCLC (N=x)	HNSCC (N=x)	XXXXX (N=x)	CC (N=x)	YYYYY (N=x)
RECIST 1.1						
BOR, n(%)						
Complete Response (CR)	X (XX.X)	X (XX.X)	X (XX.X)	X (XX.X)	X (XX.X)	X (XX.X)
Partial Response (PR)	X (XX.X)	X (XX.X)	X (XX.X)	X (XX.X)	X (XX.X)	X (XX.X)
Stable Disease (SD)	X (XX.X)	X (XX.X)	X (XX.X)	X (XX.X)	X (XX.X)	X (XX.X)
Progressive Disease (PD)	X (XX.X)	X (XX.X)	X (XX.X)	X (XX.X)	X (XX.X)	X (XX.X)
Not Evaluable	X (XX.X)	X (XX.X)	X (XX.X)	X (XX.X)	X (XX.X)	X (XX.X)
ORR n (%)	X (XX.X)	X (XX.X)	X (XX.X)	X (XX.X)	X (XX.X)	X (XX.X)
95% exact CI, %	XX.X, XX.X	XX.X, XX.X	XX.X, XX.X	XX.X, XX.X	XX.X, XX.X	XX.X, XX.X
CBR at 3 month, n(%)	X (XX.X)	X (XX.X)	X (XX.X)	X (XX.X)	X (XX.X)	X (XX.X)
95% exact CI, %	XX.X, XX.X	XX.X, XX.X	XX.X, XX.X	XX.X, XX.X	XX.X, XX.X	XX.X, XX.X
CBR at 6 month, n(%)	X (XX.X)	X (XX.X)	X (XX.X)	X (XX.X)	X (XX.X)	X (XX.X)
95% exact CI, %	XX.X, XX.X	XX.X, XX.X	XX.X, XX.X	XX.X, XX.X	XX.X, XX.X	XX.X, XX.X
CBR at 9 month, n(%)	X (XX.X)	X (XX.X)	X (XX.X)	X (XX.X)	X (XX.X)	X (XX.X)
95% exact CI, %	XX.X, XX.X	XX.X, XX.X	XX.X, XX.X	XX.X, XX.X	XX.X, XX.X	XX.X, XX.X
iRECIST						
iBOR, n(%)						
iCR	X (XX.X)	X (XX.X)	X (XX.X)	X (XX.X)	X (XX.X)	X (XX.X)
iPR	X (XX.X)	X (XX.X)	X (XX.X)	X (XX.X)	X (XX.X)	X (XX.X)
iSD	X (XX.X)	X (XX.X)	X (XX.X)	X (XX.X)	X (XX.X)	X (XX.X)
iUPD	X (XX.X)	X (XX.X)	X (XX.X)	X (XX.X)	X (XX.X)	X (XX.X)
iCPD	X (XX.X)	X (XX.X)	X (XX.X)	X (XX.X)	X (XX.X)	X (XX.X)
Not Evaluable	X (XX.X)	X (XX.X)	X (XX.X)	X (XX.X)	X (XX.X)	X (XX.X)
iORR, n(%)	X (XX.X)	X (XX.X)	X (XX.X)	X (XX.X)	X (XX.X)	X (XX.X)
95% CI, %	XX.X, XX.X	XX.X, XX.X	XX.X, XX.X	XX.X, XX.X	XX.X, XX.X	XX.X, XX.X
icBR at 3 month, n(%)	X (XX.X)	X (XX.X)	X (XX.X)	X (XX.X)	X (XX.X)	X (XX.X)
95% CI, %	XX.X, XX.X	XX.X, XX.X	XX.X, XX.X	XX.X, XX.X	XX.X, XX.X	XX.X, XX.X
icBR at 6 month, n(%)	X (XX.X)	X (XX.X)	X (XX.X)	X (XX.X)	X (XX.X)	X (XX.X)
95% exact CI, %	XX.X, XX.X	XX.X, XX.X	XX.X, XX.X	XX.X, XX.X	XX.X, XX.X	XX.X, XX.X
icBR at 9 month, n(%)	X (XX.X)	X (XX.X)	X (XX.X)	X (XX.X)	X (XX.X)	X (XX.X)
95% exact CI, %	XX.X, XX.X	XX.X, XX.X	XX.X, XX.X	XX.X, XX.X	XX.X, XX.X	XX.X, XX.X

Note: Arm A = Patients with indications for which a CPI is indicated/approved; Arm B = Patients with tumor types for which CPI therapy is not indicated/approved; RCC = Renal Cell Carcinoma; NSCLC = Non-small Cell Lung Cancer; HNSCC = Head and Neck Squamous Cell Carcinoma; XXXXX = █; CC = Colorectal Carcinoma; YYYYY = █.

Protocol: WTX-330x2101

Date: 26Feb2025

Note: Best overall response (BOR) of CR and PR per RECIST 1.1 needs to be confirmed in a subsequent assessment (≥ 4 weeks). Immune Best overall response (iBOR) per iRECIST 1.1 is the best response among all visits according to the following sequence: Immune Complete Response (iCR), Immune Partial Response (iPR), Immune Stable Disease (iSD), Immune Confirmed Progressive Disease (iCPD), Immune Unconfirmed Progressive Disease (iUPD), Not Evaluable.

Note: Overall response rate (ORR or iORR) is defined as the proportion of patients achieving CR and/or PR in RECIST 1.1 or iCR and/or iPR in iRECIST.

Note: Clinical Benefit Rate (CBR or iCBR) is defined as the proportion of subjects achieving clinical benefit, which is defined as the time from the date of last CR/PR/SD per RECIST or iCR/iPR/iSD per iRECIST to the date of first dose is at least 3, 6, or 9 months.

Protocol: WTX-330x2101

Date: 26Feb2025

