## Dose Expansion (Part 2)

Patients in Dose Expansion will have a confirmed diagnosis of a r/r locally advanced or metastatic solid tumor or lymphoma for which the patient has progressed or is intolerant of standard therapy, or for whom no standard therapy with proven benefit exists. Dose Expansion (Part 2) will be conducted in 2 arms that will enroll the following patient populations:

- **Arm A:** Patients with indications for which a CPI is indicated/approved (e.g., cutaneous malignant melanoma, RCC, non-small cell lung cancer [NSCLC], head and neck squamous cell carcinoma [HNSCC], urothelial carcinoma, etc.) who have been treated with a CPI regimen and who demonstrate primary or secondary resistance to CPI therapy. Primary resistance is defined as disease progression or stable disease (SD) < 6 months as the best response after at least 6 weeks of exposure to inhibitors of PD-(L)1. Secondary resistance is defined as disease progression  $\geq$  6 months after initiation of PD-(L)1 inhibitors in patients who have received clinical benefit (i.e., CR or PR or SD > 6 months). Patients who discontinue CPI therapy for toxicity or other reasons and who don't demonstrate primary or secondary resistance to CPIs as defined here are not eligible. Patients with Hodgkin lymphoma are also ineligible.
- **Arm B:** Patients with tumor types for which CPI therapy is not indicated/approved (e.g., pancreatic cancer, microsatellite-stable [MSS] colorectal carcinoma, castrate-resistant prostate cancer [CRPC], NHL) and who are CPI naïve. Patients with NHL should have either follicular lymphoma or diffuse large B-cell lymphoma (DLBCL), though other subtypes of NHL including T-cell lymphomas may be considered after a discussion with the Sponsor. All patients with NHL must have received at least 2 prior systemic therapies. Patients with primary CNS malignancies are not eligible.

Additional arms may be added in the Dose Expansion for specific indications of interest.

Patients will remain on study treatment until they experience unacceptable toxicity, progressive disease per RECIST ([Appendix D; Eisenhauer et al., 2009](#)) or iRECIST ([Appendix E](#)) for solid tumors, or confirmed progressive disease for NHL (dose expansion part) according to Lugano classification ([Cheson et al., 2014](#)), and/or treatment discontinued at discretion of the Investigator, or the patient withdraws consent.

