### Primary (Dose Expansion) Analysis

For primary analysis of the Dose Expansion (Part 2) cohorts, a probability of success design for the ORR based on the best overall response (BOR) will be used. To model the primary analysis of the dose expansion cohorts, 2 independent Bayesian beta binomial designs with beta (0.05, 0.95) prior distributions will be used. The response criteria for success are defined as follows: the study is considered successful in an extension arm if the posterior probability that the true response rate exceeds 10% is at least 90%. The final analysis will take place after the completion of the dose expansion cohorts when the last patient has had the final end-of-study visit.

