3.2. Dose Expansion Phase

Once the MTD and/or RDE is determined for WTX-330 as a monotherapy in the dose escalation (Part 1), the dose expansion (Part 2) with WTX-330 as a monotherapy will initiate in each of the 2 dose expansion cohorts (Arms A and B; Section 1.3.2). Cohorts of up to 20 patients each are planned for each of the dose expansion arms.

These sample sizes were selected based on practical consideration to confirm safety of WTX-330 for each indication and without formal power calculation.

To show that these sample sizes will also give early evidence on clinical benefit, Table below provides probabilities of declaring success for varying true response rate based on independent Bayesian Beta-binomial models assuming Beta (0.5, 0.5) priors for each expansion arm and declaring success if the posterior probability that the true response rate exceeds 10% is large (at least 90%). This translates to declaring success for an expansion arm if at least 4/20 are observed.

True response rate (%)	10	15	20	25	30	40	50	60
Probability of declaring success (%)	13.3	35.2	58.9	77.5	89.3	98.4	99.9	100

4. Planned Analyses

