8.3.3. Analysis of ORR and iORR

The number and percentage of subjects with BOR per RECIST 1.1, with iBOR per iRECIST, and with BOR per Lugano in each of the response categories will be summarized descriptively. ORR, iORR, and their 2-sided 95% confidence intervals being estimated with Clopper-Pearson method will be presented.

QMS Document Name: Statistical Analysis Plan Template(EN)	Page 21 of 41
QMS No (include version ref): STF-015-GL.03	Document date: 14JUL2022
CONFIDENTIAL	

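### Arm B: if NHL patients are enrolled, no rule or planned output combines RECIST 1.1 and Lugano responders into the arm-level ORR that the success rule uses

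*SAP*

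**What the plan says.** - **Population.** The protocol's Dose Expansion (Part 2) section and SAP 1.3.2 put NHL in Arm B beside solid tumors such as pancreatic and colorectal cancer: "Patients with NHL should have either follicular lymphoma or diffuse large B-cell lymphoma (DLBCL").
- **Rule.** Under Primary (Dose Expansion) Analysis the protocol says "a probability of success design for the ORR based on the best overall response (BOR) will be used", and that "the study is considered successful in an extension arm if the posterior probability that the true response rate exceeds 10% is at least 90" percent. SAP 3.2 plans up to 20 patients per arm and adds: "This translates to declaring success for an expansion arm if at least 4/20 are observed".
- **Response by criterion.** SAP 8.2.3 defines ORR per RECIST 1.1 and per Lugano. SAP 8.3.3 lists BOR per RECIST 1.1, "with iBOR per iRECIST, and with BOR per Lugano in each of the response categories will be summarized descriptively". Neither section says how the two are counted together.
- **Outputs.** Two expansion response tables are listed. Table 14.2.1.2.1 is by arm, has only RECIST 1.1 and iRECIST blocks, and carries the footnote "1] Include solid tumor only" on Arm B. Table 14.2.1.2.2 is by disease and is titled as solid tumor. No listed table gives Lugano response, an ORR over all Arm B patients, or a posterior probability.

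**The concern.** The rule needs a single count of responders and a single denominator for Arm B. As written, the only Arm B figure in the by-arm table is the solid-tumor rate. That rate has a smaller denominator than the rule assumes and leaves out any lymphoma responses. Someone applying the rule must either use the subset or improvise a pooling rule once results are known. The protocol labels this the primary analysis of the expansion part, so the count behind it should be fixed in advance.

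**Working it through.** **Inputs.** n = 20 per arm, at least 4 responders needed, and prior Beta(0.5, 0.5) (SAP 3.2: "independent Bayesian Beta-binomial models assuming Beta (0.5, 0.5) priors for each expansion arm"). The protocol gives a different prior ("2 independent Bayesian beta binomial designs with beta (0.05, 0.95) prior distributions will be used"), so both are shown. The number of NHL patients is not in the documents. It is an assumption, k, varied from 0 to 10 of 20.

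**Formulas.** With r responders among n and prior Beta(a, b), the posterior is Beta(a + r, b + n − r). Success requires P(ORR > 0.10) ≥ 0.90. The threshold t(n) is the smallest r that meets this. The probability of success at true rate p is P(X ≥ t), with X ~ Binomial(n, p).

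**Step 1: reproduce the plan.** With the SAP prior, 3/20 gives a posterior of Beta(3.5, 17.5) and P(ORR > 0.10) = 0.786, and 4/20 gives Beta(4.5, 16.5) and 0.922. The threshold of 4 is right. P(X ≥ 4) with n = 20 is 13.3, 35.2, 58.9, 77.5, 89.3, 98.4, 99.9 and 100% at the eight tabulated rates, matching SAP 3.2. With the protocol prior, 4/20 gives 0.874 and 5/20 gives 0.959, so 5 are needed.

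**Step 2: apply the rule to solid tumors only (n = 20 − k), re-deriving the threshold each time.**

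| NHL (assumed) | Solid n | SAP prior: needed | Success % at 10 / 20 / 30% | Protocol prior: needed | Success % at 10 / 20 / 30% |
|---|---|---|---|---|---|
| 0 | 20 | 4 | 13.3 / 58.9 / 89.3 | 5 | 4.3 / 37.0 / 76.2 |
| 2 | 18 | 4 | 9.8 / 49.9 / 83.5 | 4 | 9.8 / 49.9 / 83.5 |
| 5 | 15 | 4 | 5.6 / 35.2 / 70.3 | 4 | 5.6 / 35.2 / 70.3 |
| 6 | 14 | 3 | 15.8 / 55.2 / 83.9 | 4 | 4.4 / 30.2 / 64.5 |
| 8 | 12 | 3 | 11.1 / 44.2 / 74.7 | 4 | 2.6 / 20.5 / 50.7 |
| 10 | 10 | 3 | 7.0 / 32.2 / 61.7 | 3 | 7.0 / 32.2 / 61.7 |

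The effect is not smooth, because the threshold moves in whole patients. Under the SAP prior, 3/15 just misses (0.895), which makes n = 15 the worst split for 1 to 8 NHL patients. The table uses one true rate for the whole arm. If lymphoma and solid tumors respond at different rates, the gap changes.

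**Step 3: can the decision flip?**
- 2/15 solid plus 3/5 NHL is 5/20. The whole arm gives 0.977 (SAP prior) or 0.959 (protocol prior), which is success. The solid subset 2/15 gives 0.700 or 0.566, which is failure.
- 3/15 solid plus 1/5 NHL is 4/20. Under the SAP prior, the whole arm gives 0.922 (success) and the subset 0.895 (failure).
- It can also flip the other way. With the SAP prior, 3/14 solid plus 0/6 NHL meets the threshold on the subset (3 needed), but 3/20 gives 0.786 and fails.

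**The case against.** A reader might infer that the arm-level ORR is never produced, or that the primary analysis has been dropped. The documents do not support that.

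- Arm A is untouched. Its examples are solid tumors, Hodgkin lymphoma is ineligible, and its column has no such footnote.
- The SAP text does plan Lugano BOR (8.3.3) and display by arm (6.2).
- The protocol assigns RECIST to solid tumors and Lugano to NHL, so the Arm B responder count would be the sum of two non-overlapping counts.
- The modification history of the shells records a selection of outputs for the aCSR, so a missing Lugano shell does not show that the analysis was abandoned. The shell introduction still promises ORR by indication, with follicular lymphoma and DLBCL columns.
- With no NHL patients, the table already gives the full Arm B rate.

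All of this stands and limits the point to Arm B. It does not close the gap. Restoring every omitted shell would still leave two separate rates and no stated rule for adding them. The addition is also not automatic: the protocol's Efficacy Analyses define ORR by confirmed CR or PR, while SAP 8.2.2 requires confirmation for RECIST 1.1 but states none for Lugano.

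A second tempting reading is that the footnote is a mistake. It is correct for that table. The blocks are RECIST 1.1 and iRECIST, and deleting the footnote would put NHL patients into denominators to which those criteria do not apply.

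It could also be said that SAP sections 2 and 13 plan no hypothesis testing. But the protocol sets an explicit success criterion, SAP 3.2 repeats it, and SAP 1.1 declares no major change from the protocol.

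**Conclusion.** The point holds for Arm B, on condition that NHL patients are enrolled. The by-arm expansion ORR table covers a subset of the arm, and no rule joins the two response criteria. The size depends on an NHL count that the documents do not give, so no single figure should be quoted.

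At 5 NHL patients the loss under the SAP prior is 58.9 − 35.2 = 23.7 points at true ORR 20% and 89.3 − 70.3 = 19.0 points at 30%. A reader might take this as typical, but it is the unfavourable end for 1 to 8 NHL patients. At 6 the loss is 3.7 and 5.4 points. Under the protocol prior, 5 NHL patients cost 37.0 − 35.2 = 1.8 and 76.2 − 70.3 = 5.9 points, and with 2 the subset passes more often than the whole arm. What holds under either prior is that the decision can differ between the subset and the whole arm, as 5/20 against 2/15 shows. The disagreement between the two priors is a separate matter and is not settled here.

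**What to change.** 1. In SAP 8.3.3, define one responder flag per patient by the disease-appropriate criterion: RECIST 1.1 for solid tumors, Lugano for NHL.
2. State whether a Lugano CR or PR must be confirmed, reconciling the protocol's Efficacy Analyses with SAP 8.2.2. Say also which of the protocol's NHL readings (radiological, metabolic or overall) feeds the flag.
3. Compute Arm B ORR and the success rule on all efficacy-evaluable Arm B patients.
4. Add an all-Arm-B row showing that ORR and the posterior probability that it exceeds 10%.
5. Keep the footnote on the RECIST 1.1 and iRECIST blocks, and keep the by-criterion results as supportive.

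The cost is a few sentences in the SAP, one derived variable and one table row. No new data are needed. It should be settled before the final analysis.

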14.3 Summaries and Analyses of Safety

Table 14.3.1.1.1
Overall Summary of Treatment-Emergent Adverse Events - Dose Escalation
Safety Analysis Set

Subjects Who Had Any, n (%)	WTX-330 0.016 mg/kg (N=x)	WTX-330 0.032 mg/kg (N=x)	WTX-330 0.056 mg/kg (N=x)	WTX-330 0.084 mg/kg (N=x)	WTX-330 0.126 mg/kg (N=x)	WTX-330 0.190 mg/kg (N=x)	WTX-330 0.290 mg/kg (N=x)	WTX-330 0.XXX mg/kg (N=x)	Total (N=x)
TEAEs	X (XX.X)	XX (XX.X)							
TEAEs Related to WTX-330	X (XX.X)	XX (XX.X)							
Grade 3 or Higher TEAEs	X (XX.X)	XX (XX.X)							
Grade 3 or Higher TEAEs Related to WTX-330	X (XX.X)	XX (XX.X)							
Serious TEAEs	X (XX.X)	XX (XX.X)							
Serious TEAEs Related to WTX-330	X (XX.X)	XX (XX.X)							
TEAEs Leading to WTX-330 Withdrawal	X (XX.X)	XX (XX.X)							
WTX-330-Related TEAEs Leading to WTX-330 Withdrawal	X (XX.X)	XX (XX.X)							
TEAEs Leading to WTX-330 Modification	X (XX.X)	XX (XX.X)							
Dose Delayed	X (XX.X)	XX (XX.X)							
Dose Interrupted	X (XX.X)	XX (XX.X)							
Dose Reduced	X (XX.X)	XX (XX.X)							
Infusion Rate Reduced	X (XX.X)	XX (XX.X)							
WTX-330-Related TEAEs Leading to WTX-330 Modification	X (XX.X)	XX (XX.X)							
TEAEs of Special Interest	X (XX.X)	XX (XX.X)							
Immune Related TEAEs	X (XX.X)	XX (XX.X)							
Infusion Related Reaction	X (XX.X)	XX (XX.X)							
Cytokine Release Syndrome	X (XX.X)	XX (XX.X)							
DLT	X (XX.X)	XX (XX.X)							
TEAE Leading to Death	X (XX.X)	XX (XX.X)							

Note: A TEAE is defined as an AEs that emerges or worsens (ie increase in CTCAE grade) on/after the first WTX-330 dose and within 30 days of the last WTX-330 dose or the start of a new cancer regimen, whichever occurs earlier.

Note: Adverse Events are graded with CTCAE Grade 5.0, except for Cytokine Release Syndrome which is graded with ASTCT Grade.

Note: Each subject is counted only once in each category. TEAEs related to study drug are events reported with 'Definitely Related', 'Probably', 'Possibly' or missing in the relationship.

Table 14.3.1.1.2
Overall Summary of Treatment-Emergent Adverse Events - Dose Expansion
Safety Analysis Set

Subjects Who Had Any, n(%)	Arm A (N=XX)	Arm B (N=XX)	Total (N=XX)
TEAEs	X (XX.X)	X (XX.X)	XX (XX.X)
TEAEs Related to WTX-330	X (XX.X)	X (XX.X)	XX (XX.X)
Grade 3 or Higher TEAEs	X (XX.X)	X (XX.X)	XX (XX.X)
Grade 3 or Higher TEAEs Related to WTX-330	X (XX.X)	X (XX.X)	XX (XX.X)
Serious TEAEs	X (XX.X)	X (XX.X)	XX (XX.X)
Serious TEAEs Related to WTX-330	X (XX.X)	X (XX.X)	XX (XX.X)
TEAEs Leading to WTX-330 Withdrawal	X (XX.X)	X (XX.X)	XX (XX.X)
WTX-330-Related TEAEs Leading to WTX-330 Withdrawal	X (XX.X)	X (XX.X)	XX (XX.X)
TEAEs Leading to WTX-330 Modification	X (XX.X)	X (XX.X)	XX (XX.X)
Dose Delayed	X (XX.X)	X (XX.X)	XX (XX.X)
Dose Interrupted	X (XX.X)	X (XX.X)	XX (XX.X)
Dose Reduced	X (XX.X)	X (XX.X)	XX (XX.X)
Infusion Rate Reduced	X (XX.X)	X (XX.X)	XX (XX.X)
WTX-330-Related TEAEs Leading to WTX-330 Modification	X (XX.X)	X (XX.X)	XX (XX.X)
TEAEs of Special Interest	X (XX.X)	X (XX.X)	XX (XX.X)
Immune Related TEAEs	X (XX.X)	X (XX.X)	XX (XX.X)
Infusion Related Reaction	X (XX.X)	X (XX.X)	XX (XX.X)
Cytokine Release Syndrome	X (XX.X)	X (XX.X)	XX (XX.X)
TEAE Leading to Death	X (XX.X)	X (XX.X)	XX (XX.X)

Note: Arm A = Patients with indications for which a CPI is indicated/approved; Arm B = Patients with tumor types for which CPI therapy is not indicated/approved.

Note: A TEAE is defined as an AEs that emerges or worsens (ie increase in CTCAE grade) on/after the first WTX-330 dose and within 30 days of the last WTX-330 dose or the start of a new cancer regimen, whichever occurs earlier.

Note: Adverse Events are graded with CTCAE Grade 5.0, except for Cytokine Release Syndrome which is graded with ASTCT Grade.

Note: Each subject is counted only once in each category. TEAEs related to study drug are events reported with 'Definitely Related', 'Probably', 'Possibly' or missing in the relationship.

Table 14.3.2.1.1
Summary of Treatment-Emergent Adverse Events by System Organ Class and Preferred Term - Dose Escalation
Safety Analysis Set

System Organ Class/ Preferred Term	WTX-330 0.016	WTX-330 0.032	WTX-330 0.056	WTX-330 0.084	WTX-330 0.126	WTX-330 0.190	WTX-330 0.290	WTX-330 0.XXX	Total (N=x)
Patients with Any Event, n (%)	X (XX.X)	XX (XX.X)							
System Organ Class #1	X (XX.X)	XX (XX.X)							
Preferred Term #1	X (XX.X)	XX (XX.X)							
Preferred Term #2	X (XX.X)	XX (XX.X)							
<insert>	X (XX.X)	XX (XX.X)							
System Organ Class #2	X (XX.X)	XX (XX.X)							
Preferred Term #1	X (XX.X)	XX (XX.X)							
Preferred Term #2	X (XX.X)	XX (XX.X)							
<insert>	X (XX.X)	XX (XX.X)							
<insert>									

Note: Adverse Events are coded with MedDRA version 26.0.

Note: A TEAE is defined as an AEs that emerges or worsens (i.e. increase in CTCAE grade/ASTCT Grade) on/after the first WTX-330 dose and within 30 days of the last WTX-330 dose or the start of a new cancer regimen, whichever occurs earlier.

Note: Each subject is counted only once in each category. Table is sorted by System Organ Class count in total, and Preferred Term count in total within each System Organ Class.

Programming Note:

Sort by SOC count in total, and PT count in total within each SOC

Repeat table 14.3.2.1.1 for the following tables, except for the column header and footnote for Dose Expansion.

Table 14.3.2.1.2

Summary of Treatment-Emergent Adverse Events by System Organ Class and Preferred Term - Dose Expansion Safety Analysis Set

Table 14.3.2.2.1

Summary of WTX-330-related Treatment-Emergent Adverse Events by System Organ Class and Preferred Term - Dose Escalation Safety Analysis Set

Programming Note: Add “Note: TEAEs related to study drug are events reported with ‘Definitely Related’, ‘Probably’, ‘Possibly’ or missing in the relationship.”

Table 14.3.2.2.2

Summary of WTX-330-related Treatment-Emergent Adverse Events by System Organ Class and Preferred Term - Dose Expansion Safety Analysis Set

Programming Note: Add “Note: TEAEs related to study drug are events reported with ‘Definitely Related’, ‘Probably’, ‘Possibly’ or missing in the relationship.”

Table 14.3.2.3.1

Summary of Treatment-Emergent Adverse Events with Grade 3 or Higher by System Organ Class and Preferred Term - Dose Escalation Safety Analysis Set

Table 14.3.2.3.2

Summary of Treatment-Emergent Adverse Events with Grade 3 or Higher by System Organ Class and Preferred Term - Dose Expansion Safety Analysis Set

Table 14.3.2.4.1

Summary of WTX-330-related Treatment-Emergent Adverse Events with Grade 3 or Higher by System Organ Class and Preferred Term - Dose Escalation Safety Analysis Set

Programming Note: Add “Note: TEAEs related to study drug are events reported with ‘Definitely Related’, ‘Probably’, ‘Possibly’ or missing in the relationship.”

Table 14.3.2.4.2

Summary of WTX-330-related Treatment-Emergent Adverse Events with Grade 3 or Higher by System Organ Class and Preferred Term - Dose Expansion

Safety Analysis Set

Programming Note: Add “Note: TEAEs related to study drug are events reported with ‘Definitely Related’, ‘Probably’, ‘Possibly’ or missing in the relationship.”

Table 14.3.2.5.1

Summary of Treatment-Emergent Adverse Events Leading to WTX-330 Withdrawal by System Organ Class and Preferred Term - Dose Escalation

Safety Analysis Set

Table 14.3.2.5.2

Summary of Treatment-Emergent Adverse Events Leading to WTX-330 Withdrawal by System Organ Class and Preferred Term - Dose Expansion

Safety Analysis Set

Table 14.3.2.6.1

Summary of WTX-330-related Treatment-Emergent Adverse Events Leading to WTX-330 Withdrawal by System Organ Class and Preferred Term - Dose Escalation

Safety Analysis Set

Programming Note: Add “Note: TEAEs related to study drug are events reported with ‘Definitely Related’, ‘Probably’, ‘Possibly’ or missing in the relationship.”

Table 14.3.2.6.2

Summary of WTX-330-related Treatment-Emergent Adverse Events Leading to WTX-330 Withdrawal by System Organ Class and Preferred Term - Dose Expansion

Safety Analysis Set

Programming Note: Add “Note: TEAEs related to study drug are events reported with ‘Definitely Related’, ‘Probably’, ‘Possibly’ or missing in the relationship.”

Protocol: WTX-330x2101

Date: 26Feb2025

Table 14.3.2.7.1

Summary of Treatment-Emergent Adverse Events Leading to WTX-330 Modification by System Organ Class and Preferred Term - Dose Escalation Safety Analysis Set

Table 14.3.2.7.2

Summary of Treatment-Emergent Adverse Events Leading to WTX-330 Modification by System Organ Class and Preferred Term - Dose Expansion Safety Analysis Set

Table 14.3.2.8.1

Summary of WTX-330-related Treatment-Emergent Adverse Events Leading to WTX-330 Modification by System Organ Class and Preferred Term - Dose Escalation Safety Analysis Set

Programming Note: Add “Note: TEAEs related to study drug are events reported with ‘Definitely Related’, ‘Probably’, ‘Possibly’ or missing in the relationship.”

Table 14.3.2.8.2

Summary of WTX-330-related Treatment-Emergent Adverse Events Leading to WTX-330 Modification by System Organ Class and Preferred Term - Dose Expansion Safety Analysis Set

Programming Note: Add “Note: TEAEs related to study drug are events reported with ‘Definitely Related’, ‘Probably’, ‘Possibly’ or missing in the relationship.”

Table 14.3.2.9.1

Summary of Immune Related Treatment-Emergent Adverse Events by System Organ Class and Preferred Term - Dose Escalation Safety Analysis Set

Table 14.3.2.9.2

Summary of Immune Related Treatment-Emergent Adverse Events by System Organ Class and Preferred Term - Dose Expansion Safety Analysis Set

Protocol: WTX-330x2101

Date: 26Feb2025

Table 14.3.2.10.1

Summary of Treatment-Emergent Adverse Events of Infusion Related Reaction by System Organ Class and Preferred Term - Dose Escalation Safety Analysis Set

Table 14.3.2.10.2

Summary of Treatment-Emergent Adverse Events of Infusion Related Reaction by System Organ Class and Preferred Term - Dose Expansion Safety Analysis Set

Table 14.3.2.11.1

Summary of Treatment-Emergent Adverse Events of Cytokine Release Syndrome by System Organ Class and Preferred Term - Dose Escalation Safety Analysis Set

Table 14.3.2.11.2

Summary of Treatment-Emergent Adverse Events of Cytokine Release Syndrome by System Organ Class and Preferred Term - Dose Expansion Safety Analysis Set

Table 14.3.2.12.1
Summary of Treatment-Emergent Adverse Events of Special Interest by Special Interest Category
and Preferred Term - Dose Escalation
Safety Analysis Set

Special Interest Category/ Preferred Term	WTX-330 0.016 mg/kg (N=x)	WTX-330 0.032 mg/kg (N=x)	WTX-330 0.056 mg/kg (N=x)	WTX-330 0.084 mg/kg (N=x)	WTX-330 0.126 mg/kg (N=x)	WTX-330 0.190 mg/kg (N=x)	WTX-330 0.290 mg/kg (N=x)	WTX-330 0.XXX mg/kg (N=x)	Total (N=xX)
Patients with Any Event, n(%)	X (XX.X)	XX (XX.X)							
Special Interest Category#1	X (XX.X)	XX (XX.X)							
Preferred Term #1	X (XX.X)	XX (XX.X)							
Preferred Term #2	X (XX.X)	XX (XX.X)							
<insert>	X (XX.X)	XX (XX.X)							
Special Interest Category#2	X (XX.X)	XX (XX.X)							
Preferred Term #1	X (XX.X)	XX (XX.X)							
Preferred Term #2	X (XX.X)	XX (XX.X)							
<insert>	X (XX.X)	XX (XX.X)							
<insert>									

Note: Adverse Events are coded with MedDRA version 26.0.

Note: A TEAE is defined as an AEs that emerges or worsens (i.e. increase in CTCAE grade/ASTCT Grade) on/after the first WTX-330 dose and within 30 days of the last WTX-330 dose or the start of a new cancer regimen, whichever occurs earlier.

Note: Each subject is counted only once in each category. The table is sorted by Special Interest Category count in total, and Preferred Term count in total within each Special Interest Category.

Programming Note:

Sort by Special Interest Category count in total, and PT count in total within each Special Interest Category

Special Interest Category include >=Grade 2 CRS, >= Grade 3 Oral Mucositis, Hy's Law or >= Grade 3 increased ALT or AST

Table 14.3.2.12.2

Summary of Treatment-Emergent Adverse Events of Special Interest by Special Interest Category and Preferred Term - Dose Expansion Safety Analysis Set

Special Interest Category/ Preferred Term	Arm A (N=XX)	Arm B (N=XX)	Total (N=XX)
Patients with Any Event, n (%)	XX (XX.X)	XX (XX.X)	XX (XX.X)
Special Interest Category#1	XX (XX.X)	XX (XX.X)	XX (XX.X)
Preferred Term #1	XX (XX.X)	XX (XX.X)	XX (XX.X)
Preferred Term #2	XX (XX.X)	XX (XX.X)	XX (XX.X)
<insert>	XX (XX.X)	XX (XX.X)	XX (XX.X)
Special Interest Category#2	XX (XX.X)	XX (XX.X)	XX (XX.X)
Preferred Term #1	XX (XX.X)	XX (XX.X)	XX (XX.X)
Preferred Term #2	XX (XX.X)	XX (XX.X)	XX (XX.X)
<insert>	XX (XX.X)	XX (XX.X)	XX (XX.X)
<insert>			

Note: Arm A = Patients with indications for which a CPI is indicated/approved; Arm B = Patients with tumor types for which CPI therapy is not indicated/approved.

Note: Adverse Events are coded with MedDRA version 26.0.

Note: A TEAE is defined as an AEs that emerges or worsens (i.e. increase in CTCAE grade/ASTCT Grade) on/after the first WTX-330 dose and within 30 days of the last WTX-330 dose or the start of a new cancer regimen, whichever occurs earlier.

Note: Each subject is counted only once in each category. The table is sorted by Special Interest Category count in total, and Preferred Term count in total within each Special Interest Category.

Programming Note:

Sort by Special Interest Category count in total, and PT count in total within each Special Interest Category

Special Interest Category include >=Grade 2 CRS, >= Grade 3 Oral Mucositis, Hy's Law or >= Grade 3 increased ALT or AST

Table 14.3.2.13.1
Summary of Treatment-Emergent Adverse Events by System Organ Class, Preferred Term,
and Maximum CTCAE/ASTCT Grade - Dose Escalation
Safety Analysis Set

Dose Escalation - WTX-330 0.016 mg/kg (N=xx)

System Organ Class/ Preferred Term/	Maximum CTCAE/ASTCT Grade						Total
	Grade 1	Grade 2	Grade 3	Grade 4	Grade 5	Grade 3+	
Patients with Any Event, n (%)	X (XX.X)	X (XX.X)	X (XX.X)	X (XX.X)	X (XX.X)	X (XX.X)	XX (XX.X)
System Organ Class #1	X (XX.X)	X (XX.X)	X (XX.X)	X (XX.X)	X (XX.X)	X (XX.X)	XX (XX.X)
Preferred Term #1	X (XX.X)	X (XX.X)	X (XX.X)	X (XX.X)	X (XX.X)	X (XX.X)	XX (XX.X)
Preferred Term #2	X (XX.X)	X (XX.X)	X (XX.X)	X (XX.X)	X (XX.X)	X (XX.X)	XX (XX.X)
<insert>	X (XX.X)	X (XX.X)	X (XX.X)	X (XX.X)	X (XX.X)	X (XX.X)	XX (XX.X)
System Organ Class #2	X (XX.X)	X (XX.X)	X (XX.X)	X (XX.X)	X (XX.X)	X (XX.X)	XX (XX.X)
Preferred Term #1	X (XX.X)	X (XX.X)	X (XX.X)	X (XX.X)	X (XX.X)	X (XX.X)	XX (XX.X)
Preferred Term #2	X (XX.X)	X (XX.X)	X (XX.X)	X (XX.X)	X (XX.X)	X (XX.X)	XX (XX.X)
<insert>	X (XX.X)	X (XX.X)	X (XX.X)	X (XX.X)	X (XX.X)	X (XX.X)	XX (XX.X)

Note: Adverse Events are coded with MedDRA version 26.0 and graded with CTCAE Grade 5.0, except for Cytokine Release Syndrome which is graded with ASTCT Grade.

Note: A TEAE is defined as an AEs that emerges or worsens (i.e. increase in CTCAE grade/ASTCT Grade) on/after the first WTX-330 dose and within 30 days of the last WTX-330 dose or the start of a new cancer regimen, whichever occurs earlier.

Note: Each subject is counted only once at maximum CTCAE Grade in each category. Table is sorted by System Organ Class count in total, and Preferred Term count in total within each System Organ Class.

Programming note:

- Repeat all dose levels and total on a new page.

Repeat table 14.3.2.13.1 for the following tables, except for the column header and footnote for Dose Expansion.

Table 14.3.2.13.2

Summary of Treatment-Emergent Adverse Events by System Organ Class, Preferred Term,

and Maximum CTCAE/ASTCT Grade - Dose Expansion

Safety Analysis Set

Table 14.3.2.14.1

Summary of WTX-330-related Treatment-Emergent Adverse Events by System Organ Class, Preferred Term,

and Maximum CTCAE/ASTCT Grade - Dose Escalation

Safety Analysis Set

Programming Note: Add “Note: TEAEs related to study drug are events reported with ‘Definitely Related’, ‘Probably’, ‘Possibly’ or missing in the relationship.”

Table 14.3.2.14.2

Summary of WTX-330-related Treatment-Emergent Adverse Events by System Organ Class, Preferred Term,

and Maximum CTCAE/ASTCT Grade - Dose Expansion

Safety Analysis Set

Programming Note: Add “Note: TEAEs related to study drug are events reported with ‘Definitely Related’, ‘Probably’, ‘Possibly’ or missing in the relationship.”

Table 14.3.2.15.1
Summary of Treatment-Emergent Adverse Events by Preferred Term - Dose Escalation
Safety Analysis Set

Preferred Term	WTX-330 0.016 mg/kg (N=x)	WTX-330 0.032 mg/kg (N=x)	WTX-330 0.056 mg/kg (N=x)	WTX-330 0.084 mg/kg (N=x)	WTX-330 0.126 mg/kg (N=x)	WTX-330 0.190 mg/kg (N=x)	WTX-330 0.290 mg/kg (N=x)	WTX-330 0.XXX mg/kg (N=x)	Total (N=xX)
Patients with Any Event, n (%)	X (XX.X)	XX (XX.X)							
Preferred Term #1	X (XX.X)	XX (XX.X)							
Preferred Term #2	X (XX.X)	XX (XX.X)							
Preferred Term #3	X (XX.X)	XX (XX.X)							
Preferred Term #4	X (XX.X)	XX (XX.X)							
<insert>	X (XX.X)	XX (XX.X)							

Note: Adverse Events are coded with MedDRA version 26.0.

Note: A TEAE is defined as an AEs that emerges or worsens (i.e. increase in CTCAE grade/ASTCT grade) on/after the first WTX-330 dose and within 30 days of the last WTX-330 dose or the start of a new cancer regimen, whichever occurs earlier.

